2.3 Requirements of investigators and surgeons

Surgeons involved in this project were selected from each participating hospital and are skilled in cervical cancer surgery. The lead surgeon must have experience in at least 50 surgeries each for both LRH and ARH and be able to provide the medical history of these cases. The principal investigator and members of the surgical quality control team will be on site to observe each surgeon's procedure and review the unedited video of the procedure (1 ARH and 1 LRH) provided by each surgeon for surgical quality measurement and documentation to ensure the extent of surgical resection and tumor-free management of each surgeon.

3. Interventions

3.1 Overall intervention plans

Minimally invasive radical cervical cancer treatment includes laparoscopic radical cervical cancer treatment (LRH) and robotic-assisted laparoscopic radical cervical cancer treatment, either of which can be chosen by the operator. This project focuses on the survival benefit of patients after minimally invasive and open radical cervical cancer

treatment, so radical cervical cancer treatment with preservation of reproductive function will not be included. For both open and minimally invasive radical cervical cancer surgery, the operation begins with a thorough abdominal exploration, including careful exploration of the diaphragm, and any metastatic lesions and metastatic sites should be described in detail in the operative record, with biopsy for confirmative diagnosis. If intra-abdominal lesions are found, radical cervical cancer surgery should not be used and should change to palliative treatment.

Pelvic lymph node dissection should be performed during radical cervical cancer surgery. Sentinel Lymph Node Mapping (SLN) is not included in this project, since there is no sufficient evidence for its sensitivity and specificity, and also the difficulty in achieving lymph node hyperstaging considering the large sample size of this project. If the tumor is ≥ 2 cm, or if the common iliac lymph node is positive for intraoperative freezing (optional), or if the preoperative evaluation of the paraaortic lymph nodes is positive, paraaortic lymph node dissection is preferred and followed by paraaortic lymph node biopsy. When clear the para-aortic lymph nodes, the upper border reaches the level of the inferior mesenteric artery is enough. The common iliac lymph nodes should be sent separately for examination, and the resection should include both sides of the common iliac vessels, with the upper border reaching the midpoint of the bifurcation of the abdominal aorta and the common iliac vessels and the lower border reaching the level of the bifurcation of the common iliac vessels.

If definite pelvic lymph node metastasis is found intraoperatively, continuation of pelvic lymph node dissection, and even radical cervical cancer surgery is not required, but abdominal para-aortic lymph node sampling is recommended to assess the degree of disease progression and to develop subsequent radiotherapy regimens. If surgery is continued, radical cervical cancer surgery + pelvic lymph node dissection + abdominal para-aortic lymph node dissection/biopsy is recommended.

For patients randomly assigned to LRH, the surgeon should perform laparoscopic/robotic-assisted radical laparoscopic cervical cancer surgery or perform laparoscopic-assisted radical transvaginal cervical cancer surgery.

In performing radical cervical cancer surgery, the surgeon should provide detailed descriptions of the special surgical instruments used in the laparoscopic/robotic-assisted laparoscopic group. In addition, the surgeon should document the following information in the operative record:

- Time of surgery: time from the start of radical cervical cancer surgery to the closure of all abdominal puncture sites or abdominal incisions.
- Amount of intraoperative blood loss.
- Intraoperative complications.
- If patients are randomized to the laparoscopic surgery group and are converted to open surgery intraoperatively, the reasons should be recorded.

. In case of robotic-assisted laparoscopic radical cervical cancer surgery, the time required to assemble and dock the robot should be recorded in the operative record, which should be deducted from the total operative time.

. If intraoperative parietal aortic lymph node dissection is performed simultaneously, the time required for this operation should be recorded in the operative record.

The surgical approach for stage IA1 with LVSI and stage IA2 is type B (modified radical hysterectomy with bilateral pelvic lymph node dissection, i.e., resection of 1-2 cm of the parametrium and 1-2 cm of the vagina) with para-aortic lymph node dissection if necessary (surgical staging according to FIGO 2018, surgical staging according to Querleu-Morrow staging).

For stage IB1, IB2, and IIA1, the surgical approach is type C1 (radical cervical surgery with preservation of autonomic nerves + pelvic lymph node dissection, recommended for tumor diameter <2 cm) or type C2 (radical cervical surgery with bilateral pelvic lymph node dissection, resection of 3-4 cm of the parametrium and the upper 1/4 to 1/3 of the vagina) with abdominal para-aortic lymph node dissection if necessary (surgical staging according to FIGO 2018, staging according to Querleu-Morrow staging). The depth of parametrial tissue removed should be below the deep uterine vein, and if preoperative involvement of the vaginal wall is considered, 1-2 cm of parametrial tissue should be removed.

Stage IB3, IIA2 The surgical approach is type C2 (radical cervical cancer + bilateral pelvic lymph node dissection + para-aortic lymph node dissection, 3-4 cm of parametrium and upper 1/4 to 1/3 of the vagina) (surgical staging according to FIGO 2018, surgical staging according to Querleu-Morrow staging). Parametrial tissue should be removed to a depth below the deep uterine vein, and 1-2 cm of parametrial tissue should be removed if preoperative involvement of the vaginal wall is considered.

[figure not shown]

Figure 1A

[figure not shown]

Figure 1B

Figure 1A. Type B: Surgical resection range of modified radical hysterectomy

Figure 1B. Type C2: Surgical resection range radical cervical cancer

The tumor-free principle during surgery includes:

- 1) Severing the vagina before vaginal closure by: closure of the vagina with an obturator; ligature ring ligation of the vagina; transvaginal suture of the vagina.
- 2) After laparoscopic ligation of the vagina, the vagina is irrigated with sterile water, and then the vagina is severed and sutured; after open surgery, the vagina is closed with renal clamps and the anterior vaginal wall is incised, gauze is inserted, then the posterior wall is severed and the vaginal stump is sterilized.
- 3) Encourage sharp and gentle excision, and try to avoid vigorous tearing and plucking movements.
- 4) Whole lymph nodes are removed without touching other parts and placed in a specimen bag for final removal; extensive hysterectomy is performed in whole and excessive straining is avoided intraoperatively.
- 5) Rinse the instruments that have contacted the tumor in the vagina and separate them from other instruments; if suspicious metastatic tissue is encountered in the pelvic and abdominal cavity, remove it directly into the specimen bag without contacting other parts after excision.
- 6) Aspirate the pelvic and abdominal cavity after full postoperative rinsing with sterile water, and avoid backflow of pelvic rinsing fluid into the upper abdomen when the head is low and the feet are high.
- 7) Do not lift the uterus. Use other methods such as silk thread to pull the uterine body.

3.2 Standard treatment plan:

Open radical hysterectomy for cervical cancer + pelvic lymph node dissection/para-aortic lymph node dissection

- a) The preoperative prophylactic antibiotics are given at least 15 minutes before incision of the skin.
- b) The sequential compression device (antithrombotic pressure pump) is installed.
- c) The patient is placed in the supine position or bladder lithotomy position.
- d) Considering the wide range of surgical instruments used in this type of surgery, the use of laparoscopic instruments depends on the operator's personal choice.
- e) The incision is chosen as a median abdominal incision or a low transverse incision.

- f) After entering the abdomen, a thorough abdominal exploration is performed, including careful exploration of the diaphragm. Any metastatic lesions and metastatic sites should be described in detail in the surgical record, and biopsy is performed to confirm the diagnosis.
- g) The lateral pelvic peritoneum is opened and any enlarged, suspicious lymph nodes should be removed (if feasible) followed by intraoperative freezing. If these lymph nodes are positive, abdominal para-aortic lymph node biopsy should be performed, but radical cervical cancer surgery may be forgone and the treatment regimen for this patient will be switched to radical radiotherapy; or radical cervical cancer surgery + pelvic lymph node dissection + abdominal para-aortic lymph node dissection/biopsy may continue.
- h) The radical cervical cancer surgery with or without bilateral salpingo-oophorectomy will be performed if there are no suspected pelvic lymph nodes.
- i) The Removal of ovaries: the ovaries may be preserved or removed, or ovarian transposition may be performed, depending on the subject's condition.
- j) The scope of pelvic lymph node dissection: lymph nodes adjacent to the common iliac artery, external iliac artery, internal iliac artery and lymph nodes in the closed fossa should be removed.
- k) The abdominal para-aortic lymph node dissection should reach the level of the inferior mesenteric artery.
- l) Tumor-free principle: use open surgical kidney pedicle forceps to clamp the vagina close, then incision of the anterior vaginal wall, insertion of gauze, followed by severance of the posterior wall and disinfection of the vaginal stump.
- m) The abdominal drainage tube is non-compulsory and can be chosen by each center.
- n) The closure of the abdomen layers: closure of the fascia and closure of the skin.
- o) Indwelling urine catheter.

3.3 Intervention treatment:

Laparoscopic or robot-assisted laparoscopic radical hysterectomy for cervical cancer + pelvic lymph node dissection/para-aortic lymph node dissection.

- 1) The preoperative prophylactic antibiotics are given at least 15 minutes before incision of the skin.
- 2) The sequential compression device (antithrombotic pressure pump) is installed.
- 3) The patient is placed in bladder lithotomy position with the upper arms flat on the sides of the body or on the chest.
- 4) The choice of laparoscopic instruments depends on the surgeon's personal preference,

considering the wide range of surgical instruments used for this type of procedure.

- 5) The approach to the abdomen and the number of puncture points for laparoscopic surgery depend on the operator's personal choice.
- 6) After entering the abdomen, a thorough abdominal exploration, including careful exploration of the diaphragm, should be performed first. Any metastatic lesions and metastatic sites should be described in detail in the operative record, and a biopsy should be performed to clarify the diagnosis.
- 7) The round ligament is separated in order to open the retroperitoneum. The lateral pelvic peritoneum is opened and any enlarged, suspected lymph nodes should be resected (if feasible) followed by intraoperative cryopexy. If these lymph nodes are positive, abdominal para-aortic lymph node biopsy should be performed, but radical cervical cancer surgery may be forgone and the treatment plan will be changed to radical radiotherapy in this subject; or radical cervical cancer surgery + pelvic lymph node resection + abdominal para-aortic lymph node dissection/biopsy may be continued.
- 8) The radical cervical cancer surgery with or without bilateral salpingo-oophorectomy will be performed if there are no suspected pelvic lymph nodes.
- 9) The removal of ovaries: the ovaries may be preserved or removed or ovarian transposition may be performed depending on the patient's specific situation.
- 10) The scope of pelvic lymph node resection: the lymph nodes adjacent to the common iliac artery, external iliac artery, internal iliac artery and the lymph nodes in the closed fossa should be removed.
- 11) The uterus is not lifted, and methods such as silk traction of the uterine body are used.
- 12) The uterine artery is identified and dissociated at the point where the internal iliac artery divides from the uterine artery.
- 13) The parametrial tissue and the uterosacral ligament are excised to ensure adequate surgical margins. Paying attention to the tumor- free principle, the vagina is closed before severing it, which can be done by: closure of the vagina with an obturator; closure of the vagina with a ligature ring; and closure of the vagina with transvaginal sutures. After laparoscopic closure of the vagina, the vagina is irrigated with sterile water, after which the vagina is severed and the vaginal stump is sutured.
- 14) Systematic lymphadenectomy: removal of lymph nodes adjacent to the common iliac artery, external iliac artery, internal iliac artery and lymph nodes in the closed fossa ± parietal aortic lymph nodes (up to the level of the inferior mesenteric artery).
- 15) The intraoperative lymph nodes are removed by en bloc resection, without touching other parts, and will be placed in a specimen bag for final removal.

- 16) The postoperative pelvic and abdominal cavity will be suctioned after full flushing with sterile water, and the pelvic flushing fluid should be avoided to back up into the upper abdomen during trendelenburg position.
- 17) Use of a vaginal apex closure device can be chosen by each surgeon.
- 18) The laparoscopic operation can also be performed through vagina.

3.4 Intraoperative sentinel lymph node localization biopsy:

Sentinel lymph node localization biopsy will not be used in this project.

3.5 Pelvic/Para-aortic lymphadenectomy:

The surgeon is required to perform pelvic lymphadenectomy \pm para-aortic lymphadenectomy in both groups of patients; however, the surgeon may also choose not to perform lymphadenectomy if the patient meets the following criteria:

- 1) Morbid obesity: (European and American criteria: weight over 100 pounds or $BMI \geq 40$) $BMI \geq 37.5$ for the Asian population; or $BMI \geq 32.5$ with two or more metabolic complications.
- 2) Requires blood thinning medication.
- 3) The patient's physical condition is not suitable for lymphadenectomy from a medical safety perspective.

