Supplementary therapy will be administered according to the postoperative pathological findings of the patients. Those with high-risk factors who have positive parametrium will be supplemented with external pelvic irradiation therapy + cisplatin/carboplatin concurrent chemotherapy, those with positive vaginal margins will be selected for external pelvic irradiation therapy + retrovaginal radiotherapy + cisplatin/carboplatin concurrent chemotherapy, and those with positive pelvic lymph nodes will be treated with 1 course of systemic chemotherapy + external pelvic irradiation radiotherapy ± extended field radiotherapy adjacent to the abdominal aorta + cisplatin concurrent chemotherapy + 3-6 courses of adjuvant systemic chemotherapy after radiotherapy. Those with intermediate risk factors will be treated with external pelvic irradiation radiotherapy + cisplatin concurrent chemotherapy, and those with positive proximal margins will be treated with external pelvic irradiation radiotherapy EBRT + cisplatin concurrent chemotherapy + retrovaginal radiotherapy. Targeted immunotherapeutic agents such as bevacizumab and PD-1, which have just obtained some results in clinical studies, are not considered in this trial for the time being. It could be used according doctor's orders.

3.10 Outcome measurements:

- 1) Main outcome indicators: 5-year OS.
- 2) Secondary outcome measurements: 5-year PFS, refer to RECIST criteria.
- 3) Other outcome measurements: operation time, anesthesia time, intraoperative bleeding volume, intraoperative complications, postoperative complications, postoperative pain score, postoperative hospital stay, one-month postoperative survival quality, one-year postoperative survival quality, sexual quality of life.
- 4) Other evaluation parameters: patient's demographic characteristics, signs and symptoms, stage, pathological type, tumor site, comorbidities, medical history, length of hospital stay and cost.
- 5) This study intends to sample and collect intraoperative tumor tissues from tumor patients and evaluate specific tumor stages with genetic testing to guide later treatments such as targeted or immune therapies. Histological studies and molecular studies will also be conducted.

	Pre-phase	0-12 months	12-24 months	24-36 months	36-60 months
Meet the researchers	X				
Obtain IRB approval	X				
Funding application	X				
Enrollment of study patients		X	X	X	
Data monitoring		X	X	X	X
Data collection		X	X	X	X
Data analysis					X

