5.3.3 Secondary outcome analysis

a) The rate of PFS at 5 years:

Cox proportional hazards model will be used to estimate the hazard ratio and 95% CI for the effect of treatment on the 5-year PFS rate.

b) Analysis of continuous outcomes:

The continuous outcomes include operative duration, anesthesia time, blood loss during operation, postoperative pain score and postoperative hospital stay. The outcomes with normal distribution will be summarised using mean and standard deviation (SD), while the outcomes with non-normal distribution will be summarised using median and interquartile. The differences in the outcomes and 95% CIs will be analysed by generalised linear model (GLM) with treatment as fixed effect and with normal distribution and identity link function.

c) Analysis of binary outcomes:

The intraoperative complications, postoperative complications, one-month and one-year postoperative quality of life and sexual life will be treated as binary outcomes, and will

be summarised by number (%) of participants with the event. The differences in the outcomes and 95% CIs will be analysed by GLM with treatment as fixed effect and with binomial distribution and identity link function.

d) Interim analysis

The O'Brien Fleming method will be used to conduct an interim analysis three years after the study. If the study has conducted only once interim analysis, the α level will be set as 0.048 in the final analysis.

4. Safety analysis

Adverse events (AEs) will be summarised using the number of AEs, the number (%) of participants with AEs by groups.

5. All analyses will be performed with a two-sided significance level of 0.05 and conducted using SAS software, version 9.4 (SAS Institute).

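### Robot assembly and docking time is deducted from operative time in robotic cases only, so the two arms are not compared on one definition of operative duration

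*Combined protocol and SAP*

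**What the plan says.** The list of items for the operative record in section 3.1 defines the measure for both arms: "Time of surgery: time from the start of radical cervical cancer surgery to the closure of all abdominal puncture sites or abdominal incisions". Further down the same list comes the exception: "In case of robotic-assisted laparoscopic radical cervical cancer surgery, the time required to assemble and dock the robot should be recorded in the operative record", followed by the instruction "which should be deducted from the total operative time".

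The next item concerns para-aortic lymph node dissection performed in the same operation. There, "the time required for this operation should be recorded in the operative record", and no deduction is mentioned. None is mentioned for opening the abdomen or for placing conventional laparoscopic ports.

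Robotic assistance is one of the two forms of the minimally invasive procedure in section 3.1, "either of which can be chosen by the operator". The open procedure in section 3.2 has no robotic form.

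Section 3.10 places operative time among the other outcomes, below primary overall survival and secondary progression-free survival: "operation time, anesthesia time, intraoperative bleeding volume". Section 5.3.3 b) makes it a between-arm comparison: "The continuous outcomes include operative duration, anesthesia time, blood loss during operation, postoperative pain score and postoperative hospital stay". The difference and its 95% confidence interval come from a Gaussian linear model in which treatment is the only term named. No term for robotic use and no analysis of undeducted time are planned. Section 5.3.2 c) also uses operative duration as a covariate in an adjusted Cox model for overall survival.

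**The concern.** A difference between randomised arms is interpretable when the outcome is measured in the same way in both. Here one component of time is removed from some patients in one arm, and no matching component is removed in the other. The resulting difference mixes any true difference in operating time with an effect of the measurement rule.

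The rule also has a direction. A deduction can shorten recorded time but never lengthen it, and it can apply only in the minimally invasive arm. How far it moves the mean depends on how many operators choose the robot, which randomisation does not control. What is at stake is the reported difference in operative duration, an outcome on which surgical routes are commonly compared.

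**Working it through.** The documents state no expected value, standard deviation (SD) or target difference for operative time, so there is no figure of the plan's own to reproduce. The check has two parts.

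**1. The rule by type of case (section 3.1)**

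| Case | Arm | Time removed |
|---|---|---|
| Open | Open | None stated |
| Conventional laparoscopic | Minimally invasive | None stated |
| Robotic-assisted | Minimally invasive | Assembly and docking |
| Any, with para-aortic dissection | Either | None stated; time recorded separately |

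Let *r* be the robotic share of the minimally invasive arm and *d* the mean minutes deducted per robotic case. The deduction lowers that arm's mean by *r* × *d* and leaves the open arm's mean unchanged. This is zero when *r* = 0 and otherwise has one sign.

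**2. Illustrative size**

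Neither *r* nor *d* is in the documents. With assumed values, the shift in minutes is:

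| Robotic share | d = 10 | d = 20 | d = 30 |
|---|---|---|---|
| 0% | 0 | 0 | 0 |
| 10% | 1 | 2 | 3 |
| 25% | 2.5 | 5 | 7.5 |
| 50% | 5 | 10 | 15 |

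The 1-15 minute range runs from 10% × 10 = 1 to 50% × 30 = 15. If every case were robotic, the shift would be 10 to 30 minutes.

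To compare these shifts with the precision of the comparison, take 552 patients per arm (section 3.12) and a further assumption, an SD of 40 to 60 minutes:

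- Standard error = SD × √(2/552) = SD × 0.0602, which is 2.41 minutes at SD 40 and 3.61 at SD 60.
- 95% confidence interval half-width = 1.96 × standard error, which is 4.7 minutes at SD 40 and 7.1 at SD 60.
- Suppose there is no true difference. The chance of a two-sided 5% result in favour of the minimally invasive arm is Φ(shift / standard error − 1.96). This is 2.5% when the shift is zero.

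| Shift (minutes) | SD 60 | SD 40 |
|---|---|---|
| 1 | 5% | 6% |
| 3 | 13% | 24% |
| 5 | 28% | 55% |
| 10 | 79% | 99% |

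For a 5-minute shift at SD 40, 5 / 2.41 − 1.96 = 0.12 and Φ(0.12) = 0.55. So the rule could be barely visible at a low robotic share, or could produce an apparent advantage by itself at a moderate one. The documents do not say which applies.

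**The case against.** **The deduction is open and pre-specified.** Net surgical time is a legitimate quantity, and no other part of the documents says that gross time is the target. This stands as a defence of reporting docking-excluded time. It does not make that time comparable with an open-arm time from which nothing is removed.

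**The start of the clock is unclear.** Section 3.1 counts from the start of the radical surgery and elsewhere has the operation begin with abdominal exploration. It does not say whether docking falls before or after that start. If docking comes before it, and the instruction only keeps docking out of the total, nothing is lost from start-to-closure time. If docking comes before it and is still subtracted, time that was never counted is removed. This objection stands and shapes the remedy: deleting the deduction is not enough without an explicit start point. No reading makes the deduction work against the minimally invasive arm.

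**The link to the analysis is inferred.** Sections 5.3.2 and 5.3.3 do not define operative duration, and a detailed SAP is still to be written (sections 5.2.1 and 5.3.1). That is correct, but section 3.1 gives the only definition in the documents, so it is the one an analyst would use.

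**Partial safeguards exist.** Anesthesia time is compared between arms with no stated deduction, and recorded docking minutes allow undeducted time to be rebuilt. Both help a reader and make the fix cheap, but neither corrects the planned comparison.

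**Stronger readings that a reader might infer.** One is that the adjusted survival model is materially distorted. The documents do not support this: nothing shows that a few minutes would change the hazard ratio, and adjusting for a variable measured after randomisation is open to question however it is timed. Another is that the rule undermines the cost assessment. Cost effectiveness is a secondary objective, but section 3.10 records cost and hospital stay directly, section IX deals with household income and reimbursement, and nothing uses operative time as a cost input.

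**Conclusion.** The point holds as a minor defect in the definition of one non-primary outcome. As written, operative duration is measured differently in robotic cases, which occur in one arm only. To the extent that robots are used, the difference can shift only towards the minimally invasive arm, by robotic share times mean docking minutes.

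The direction follows from the text, assuming that the analysed variable is the one defined in section 3.1. The size does not: 1-15 minutes rests wholly on assumed shares and docking times, and the significance rates also rest on an assumed SD. It would be wrong to say that the rule always favours the minimally invasive arm, because the documents give no robotic share and the shift is zero without robotic cases. The primary unadjusted comparison of 5-year overall survival does not use operative time and is unaffected.

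**What to change.** In section 3.1, and in the detailed SAP when it is written, define operative time by one explicit start point (for example first skin incision) and one stop point (final closure of all puncture sites or incisions), identical for every patient. Use that undeducted time as operative duration in section 5.3.3. Report docking time separately and, if wanted, docking-excluded time as a labelled supplementary figure. State whether each centre's operative record holds gross or net time, so that sites do not differ. Settle this before database lock, so that the choice cannot appear to depend on the results.

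The cost is a change of wording plus a check that the start and stop times are captured; docking minutes must already be recorded. There are no extra patients or procedures. The downside is that operative time may look slightly less favourable for the robotic route.
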